6.3.4 Microbiological Response Definitions

6.3.4.1 Per-Pathogen Microbiological Response

A microbiological outcome at the TOC visit will be determined in the mMITT and ME populations for each pathogen isolated at baseline (see

[Table 7](#)). Microbiological outcome categories are eradication, presumed eradication, persistence, presumed persistence, and indeterminate, as defined in the table below. Favourable microbiological outcomes are eradication or presumed eradication. Unfavourable microbiological outcomes are persistence or presumed persistence.

Table 7 Microbiological Outcome Categories

Outcome ^a	Definition	
Favourable	Eradication	An adequate source specimen ^b demonstrates absence of the original baseline pathogen.
	Presumed eradication	An adequate source specimen ^b was not available to culture and the patient was assessed as a clinical cure.
Unfavourable	Persistence	Source specimen demonstrates continued presence of the original baseline pathogen.
	Presumed persistence	An adequate source specimen ^b was not available to culture and the patient was assessed as a clinical failure.
Indeterminate	Indeterminate	An adequate source specimen ^b was not available to culture and the patient's clinical response was assessed as indeterminate.

^a The microbiological outcomes at TOC are only applicable to patients who are not clinical failures at EOT. Patients who are failures at EOT will have the corresponding microbiological outcome determined from EOT cultures and carried forward to TOC. If no EOT culture is available for patients who are clinical failures at EOT, then the microbiological outcome at TOC will be presumed persistence. Otherwise, the microbiological outcome at TOC will be determined from cultures obtained at the TOC visit window. If no culture is available in the TOC window then the microbiological outcome at TOC will be presumed from the clinical response (see [Table 5](#)) at TOC.

^b An adequate source specimen is defined as any sample that may yield the growth of a CABP pathogen eg, blood, respiratory specimens, or pleural fluid.

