Note: For the special case of pneumococcal infection identified via a urinary antigen test only, the microbiological outcome will always be presumed from the clinical outcome (see [Table 5](#)), unless a post-baseline respiratory culture is positive for *Streptococcus pneumoniae*, in which case the microbiological outcome will be persistence. For patients with co-infection with an atypical, the outcome for atypical pathogens will be presumed from the clinical response (see [Table 5](#)).

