 - If deemed a treatment failure, or if results from previous sample test positive (rather than daily), obtain a blood culture until sterilization is confirmed in those patients with a positive result at baseline (ie, baseline blood culture grows an organism other than those judged to be transient or resident skin flora). Obtain one aerobic and one anaerobic bottle of blood from two separate sites for a total of four bottles. Perform culture and susceptibility testing at the local laboratory and send isolates, other than those judged to be transient or resident skin flora, to the central laboratory for confirmation of organism identity and susceptibility. Susceptibility testing of all isolates sent to the central laboratory will be performed by broth microdilution tests and CLSI disk diffusion tests (see Section 6.3.1.4)

Refer to the Laboratory Manual for specific procedures pertaining to the collection, processing, storage, and shipment of all specimens / cultures.

14. Determine clinical outcome according to Section 6.3.2.

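### Table 7 accepts any specimen type as proof of eradication, so a clinical failure with a sputum-only pathogen can be scored favourable on a negative blood culture

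*Protocol*

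**What the plan says.** All references are to the Protocol.

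- **Eradication (Section 6.3.4.1, Table 7).** The row is met when an adequate source specimen "demonstrates absence of the original baseline pathogen". Clinical cure is not a condition.
- **Adequate source specimen (footnote b to Table 7).** The definition reads: "An adequate source specimen is defined as any sample that may yield the growth of a CABP pathogen". The examples that follow are blood, samples from the airways and fluid from the pleura.
- **Presumed persistence (Table 7).** The row is met only when an adequate source specimen "was not available to culture and the patient was assessed as a clinical failure".
- **Failures at EOT (Table 7, footnote a).** "Patients who are failures at EOT will have the corresponding microbiological outcome determined from EOT cultures and carried forward to TOC". The fallback is: "If no EOT culture is available for patients who are clinical failures at EOT, then the microbiological outcome at TOC will be presumed persistence". Other patients are scored from cultures in the TOC window.
- **When blood is cultured.** Table 1 footnote y lists a blood culture at EOT for patients deemed failures there, and at TOC for new failures. Appendix H Section 1.5 has a related instruction: "If deemed a treatment failure, or if results from previous sample test positive (rather than daily), obtain a blood culture". Section 6.3.1.3, the heading of item 13 in Appendix H Section 1.5, and Section 12.1.1.5 (for TOC) instead make cultures depend on medical indication.
- **When sputum is cultured.** Table 1 footnote w and Section 6.3.1.1 also ask for sputum from patients deemed failures at EOT or newly at TOC.
- **Shielded cases (note after Table 7).** For pneumococcus found by urinary antigen alone, "the microbiological outcome will always be presumed from the clinical outcome", unless a later respiratory culture grows it. Atypical co-pathogens are likewise scored from clinical response.
- **Use.** Section 6.3.4.2 calls a patient favourable if every baseline pathogen is favourable. Section 12.2.2.2 and Table 10 make the per-patient and per-pathogen results in mMITT and ME secondary endpoints.

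**The concern.** If a pathogen grew in sputum but not in blood at baseline, a negative blood culture at the time of failure says almost nothing about clearance from the lung. It was negative before treatment as well. Under footnote b that culture nevertheless satisfies the eradication row. Because a culture exists, it also closes the route to presumed persistence.

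For cultured pathogens the error runs one way, from clinical failure to microbiological success. It raises the favourable rate. If it occurs about equally often in both arms, it also pulls the difference towards zero, which is the flattering direction when the trial's aim is to show similarity.

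The protocol guards against this elsewhere. The urinary-antigen note does not let a negative culture count as eradication, and Table 8 ties recurrence to the original site of infection. Patients diagnosed by sputum culture get neither safeguard in Table 7.

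**Working it through.** **Step 1. The plan's own figure.** No size or power figure is given for the microbiological endpoints. The sample size in Section 12.3 is reproduced only to show that it stands apart from this point. Per arm, n = (1.960 + 1.282)² × (0.85 × 0.15 + 0.85 × 0.15) / 0.10² = 268 evaluable. Then 268 / 0.775 = 345.8, rounded up to 346 per arm, or 692 in total. This matches the protocol. Table 7 does not enter it.

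**Step 2. Follow one patient through the rules.** At baseline *S. pneumoniae* grows in sputum and blood is sterile. At EOT the patient is a clinical failure, no sputum is obtained, and blood is negative.

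1. Footnote a: score from EOT cultures. One exists (blood), so the fallback to presumed persistence is not triggered.
2. Footnote b: blood is an adequate source specimen.
3. Eradication row: that specimen lacks the baseline pathogen, so the row is met.
4. Presumed persistence row: requires that no adequate specimen was available, so it is not met.
5. Section 6.3.4.2: with no other baseline pathogen, the patient counts as favourable.

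Had no blood been drawn, the same patient would be scored presumed persistence. The outcome turns on whether an uninformative sample was taken.

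**Step 3. Mixed results at one visit.** If sputum is positive and blood negative, the wording of both the eradication and persistence rows can be applied. Table 7 gives no order of precedence.

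**Step 4. Size, as an illustration.** Inputs:

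- c, the clinical cure rate: 85%, the Section 12.3 planning value for the CE population, carried over to mMITT and ME as an assumption;
- q, the share of clinical failures with a sputum-only pathogen, a negative blood culture and no respiratory specimen at the scoring visit. The protocol gives no q, so the range below is assumed.

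The calculation takes cures as favourable and all other failures as unfavourable.

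Favourable rate = c + (1 − c) × q, so inflation at c = 85% is 15 × q points. With equal q in both arms, the difference becomes (true difference) × (1 − q).

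| q | Favourable rate at c = 85% | Inflation (points) | A 10-point deficit (75% v 85%) appears as |
|---|---|---|---|
| 0 | 85% | 0 | −10.0 |
| 25% | 88.75% | 3.75 | −7.5 |
| 50% | 92.5% | 7.5 | −5.0 |
| 75% | 96.25% | 11.25 | −2.5 |

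For the q = 50% row: 85 + 15 × 0.5 = 92.5 in one arm, 75 + 25 × 0.5 = 87.5 in the other, difference −5.0.

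If q differs between arms, the shift need not be towards zero. With 85% cure in both arms, the spurious difference is 15 × (q in the ceftaroline arm − q in the ceftriaxone arm) points.

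**The case against.** The other side has several good points.

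- **Not every failure has a blood culture.** A reader might infer from Table 1 footnote y and Appendix H that blood is drawn in all clinical failures. The documents do not support that. Section 6.3.1.3, Section 12.1.1.5 and the heading of item 13 in Appendix H Section 1.5 refer to medical indication. The Appendix H sentence goes on to speak of confirming sterilization in patients positive at baseline, so it can be read as limited to bacteraemic patients, for whom blood is the matching site. A failure by death may leave no culture. This stands: the passages conflict and must be reconciled.
- **Sputum is requested from the same failures.** This also stands. The clear misclassification is confined to failures with a sputum-only pathogen, a negative blood culture and no respiratory specimen.
- **A positive sputum should settle a mixed result.** One can argue that absence is not demonstrated while any culture is positive, and that the persistence row does not require the specimen to be adequate. That is a sensible reading and a SAP may adopt it. It does not help the patient in Step 2, who has no sputum.
- **Some failures may truly be cleared.** Clinical failure includes treatment-limiting adverse events. This stands, so the table shows departure from the presumed outcome, not from a known truth.
- **The word source implies the same site.** That may have been the intent, but footnote b defines the term and does not say so.
- **Section 12.1.1.5 falls back on clinical response when no suitable specimen can be collected.** It leaves suitable undefined and does not override footnote b.
- **Clinical cure is reported in the same populations without using Table 7.** Discordance would therefore be visible. This lowers the stakes but does not correct the endpoint.

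**Conclusion.** The rule is wrong as written. A clinical failure with a sputum-only baseline pathogen, a negative blood culture and no follow-up respiratory specimen is scored as eradication and cannot be scored as presumed persistence. That follows from Table 7 and its footnotes alone. The protocol fixes the definition, so a SAP that followed it would reproduce the error.

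The size is unknown. Inflation is 15q points if 15% of patients fail, and q may be small because sputum is also sought. Attenuation of the treatment difference by 1 − q further assumes a similar q in both arms.

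A reader might infer that the non-inferiority conclusion is at risk. It is not: clinical cure at TOC in the CE population, its −10% criterion and the 692 patients do not depend on Table 7. The affected results are the secondary per-patient and per-pathogen microbiological endpoints in mMITT and ME, for which the protocol plans confidence intervals but states no margin or success rule. This should be fixed, but it is not essential to the trial's main conclusion.

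**What to change.** Amend Table 7 and footnote b, before unblinding, along these lines:

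1. Eradication requires a negative culture at the scoring visit (EOT for failures at EOT, otherwise the TOC window) from the same site type that yielded the baseline pathogen: respiratory, blood or pleural. If more than one site type was positive at baseline, each must be negative.
2. A culture positive for the baseline pathogen at that scoring visit is persistence, whatever other cultures show.
3. If the required same-site specimens are not available at the scoring visit and no culture there is positive, the outcome is presumed from clinical response.

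The override in item 2 must stay limited to the scoring visit. Section 6.3.1.3 calls for repeat blood cultures until sterile. If any positive post-baseline culture counted, a bacteraemic patient with a positive early repeat who later cleared and was cured would be scored as persistence.

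Separately, reconcile Table 1 footnote y, Section 6.3.1.3, Section 12.1.1.5 and Appendix H on when post-baseline blood cultures are taken.

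The cost is one footnote and one derivation rule, with no extra samples. The price is somewhat lower favourable rates, and more outcomes that are presumed from clinical response instead of read from a culture.

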6.3.4.2 Per-Patient Microbiological Response

Per-patient microbiological response at the TOC visit will be determined in the mMITT and ME Populations based on individual outcomes for each baseline pathogen. In order for a patient to have a favourable microbiological response, the outcome for each baseline pathogen must be favourable (eradicated or presumed eradicated). If the outcome for any pathogen is unfavourable (persistence or presumed persistence), the patient will be considered to have an unfavourable microbiological response.

6.3.4.3 Microbiological Categories for Pathogens Identified After Baseline Assessment

Microbiological categories for pathogens identified after the baseline assessment are super-infection, new infection, colonization, and re-infection or recurrence, as defined in [Table 8](#).

Table 8 Categorization of Bacterial Pathogens Identified After Baseline Assessment

Super-infection	Isolation of a new pathogen(s) (other than the original baseline pathogen(s)) during the period up to and including EOT from cultures of the original CABP, or a new CABP at the same site, regardless of susceptibility to study drugs, in a patient who has signs and symptoms of infection requiring alternative antimicrobial therapy.
New Infection	Isolation of a new pathogen (other than the original baseline pathogen) determined at TOC or LFU regardless of susceptibility to study drugs, in a patient who has signs and symptoms of infection requiring alternative antimicrobial therapy
Colonization	Isolation of an organism from the original CABP site that is not associated with signs and symptoms of active infection and does not require antimicrobial therapy. Colonization will be determined only at EOT and TOC when an assessment of clinical response is performed.
Microbiologic re-infection or recurrence	Isolation of a baseline pathogen from the original CABP site, at the LFU visit, in patients who had favourable clinical and microbiological responses at TOC. To be defined as a recurrent infection, pathogens must be associated with emergence or worsening of clinical signs and symptoms, with or without laboratory evidence of active infection, and require antimicrobial therapy.

6.3.5 Overall Clinical and Radiographic Response Definition

Overall response (clinical and radiographic response, see [Table 5](#) and [Table 6](#)) will be determined at the TOC visit. It will be classified as ‘success’ or ‘failure’ with an overall favourable response, ‘success’, defined as clinical cure and either radiographic success or radiographic indeterminate.

6.4 Safety

The Principal Investigator is responsible for ensuring that all staff involved in the study is familiar with the content of this section.

6.4.1 Definition of adverse events

An adverse event is the development of an undesirable medical condition or the deterioration of a pre-existing medical condition from the signing of the informed consent, whether or not considered causally related to the product. An undesirable medical condition can be symptoms (eg, nausea, chest pain), signs (eg, tachycardia, enlarged liver) or the abnormal results of an investigation (eg, laboratory findings, electrocardiogram). In clinical studies, an AE can include an undesirable medical condition occurring at any time, including run-in or washout periods, even if no study treatment has been administered. AEs may also include complications that occur as a result of protocol mandated procedures and distinguished as such.

The term AE is used to include both serious and non-serious AEs.

6.4.2 Definitions of serious adverse event

A serious adverse event is an AE occurring during any study phase (ie, run-in, treatment, washout, follow-up), that fulfils one or more of the following criteria:

- Results in death
- Is immediately life-threatening
- Requires in-patient hospitalisation or prolongation of existing hospitalisation
- Results in persistent or significant disability or incapacity
- Is a congenital abnormality or birth defect
- Is an important medical event that may jeopardise the patient or may require medical intervention to prevent one of the outcomes listed above.

For further guidance on the definition of a SAE, see [Appendix B](#).

6.4.3 Recording of adverse events

Time period for collection of adverse events

Adverse Events will be collected from time of signature of informed consent throughout the treatment period up to and including the TOC visit. SAEs will be collected from time of signature of informed consent throughout the treatment period up to and including the LFU visit.

Follow-up of unresolved adverse events

Any AE(s) that is unresolved at the LFU visit is followed up by the investigator for as long as medically indicated, but without further recording in the eCRF. AstraZeneca retains the right to request additional information for any patient with ongoing AE(s)/SAE(s) at the end of the study, if judged necessary.

Variables

The following variables will be collect for each AE:

- AE (verbatim)
- Date and time when the AE started and stopped
- Intensity (rating scale for in-patients)
 - Mild (awareness of sign or symptom, but easily tolerated)
 - Moderate (disturbing but still tolerable)
 - Severe (intolerable)
- Whether the AE is serious or not
- Investigator causality rating against the Investigational Product (yes or no)
- Action taken with regard to investigational product
- AE caused patient's withdrawal from study (yes or no)
- Outcome.

In addition, the following variables will be collected for SAEs, as appropriate:

- Date AE met criteria for serious AE
- Date Investigator became aware of serious AE
- AE is serious due to
- Date of hospitalisation
- Date of discharge
- Probable cause of death
- Date of death
- Autopsy performed
- Causality assessment in relation to Study procedure(s)
- Causality assessment in relation to Other medication

- Causality assessment in relation to Additional Study Drug
- Description of AE

It is important to distinguish between serious and severe AEs. Severity is a measure of intensity whereas seriousness is defined by the criteria in Section 6.4.2. An AE of severe intensity need not necessarily be considered serious. For example, nausea that persists for several hours may be considered severe nausea, but not a SAE. On the other hand, a stroke that results in only a limited degree of disability may be considered a mild stroke but would be a SAE.

Additional information will be requested and collected when an AE of seizure, haemolytic anaemia, acute renal failure and DILI (drug-induced liver injury) is reported, irrespective of seriousness. For Cases of Potential Hy's Law (increase in both AST or ALT ≥ 3 xULN and total bilirubin ≥ 2 xULN), additional information will be requested and collected.

Intolerability of the Study Treatment

All AEs that, in the opinion of the Investigator, may represent intolerance of the study treatment and/or their administration must be marked as such on the AE eCRF. In general, these events will be temporally related to the study treatment. Examples of possible systemic reactions representing intolerability of the study treatment are fever, flushing, or nausea temporally related to the study treatment. Examples of local infusion site reactions are erythema, pain, induration swelling, or phlebitis at the infusion site. These systemic and local reactions must be recorded in the AE eCRF. For local reactions the investigator will distinguish those AEs which are related to mechanical infusion malfunction and/or administration technique from those which are related to the administration of the study treatment itself and recorded as such on the eCRF.

Causality collection

The Investigator will assess causal relationship between Investigational Product and each Adverse Event, and answer 'yes' or 'no' to the question 'Do you consider that there is a reasonable possibility that the event may have been caused by the investigational product?'

For SAEs causal relationship will also be assessed for other medication, including comparator, and study procedures. Note that for SAEs that could be associated with any study procedure the causal relationship is implied as 'yes'.

A guide to the interpretation of the causality question is found in [Appendix B](#).

Adverse Events based on signs and symptoms

All AEs spontaneously reported by the patient or reported in response to the open question from the study personnel: 'Have you had any health problems since the previous visit/you were last asked?', or revealed by observation will be collected and recorded in the CRF. When collecting AEs, the recording of diagnoses is preferred (when possible) to recording a list of

signs and symptoms. However, if a diagnosis is known and there are other signs or symptoms that are not generally part of the diagnosis, the diagnosis and each sign or symptom will be recorded separately.

Adverse Events based on examinations and tests

The results from protocol mandated laboratory tests and vital signs will be summarised in the clinical study report. Deterioration as compared to baseline in protocol-mandated laboratory values, vital signs, and 12-lead ECGs findings should therefore only be reported as AEs if they fulfil any of the SAE criteria or are the reason for discontinuation of treatment with the investigational product.

If deterioration in a laboratory value/vital sign is associated with clinical signs and symptoms, the sign or symptom will be reported as an AE and the associated laboratory result/vital sign will be considered as additional information. Wherever possible the reporting investigator uses the clinical, rather than the laboratory term (eg, anaemia versus low haemoglobin value). In the absence of clinical signs or symptoms, clinically relevant deteriorations in non-mandated parameters should be reported as AE(s).

Any new or aggravated clinically relevant abnormal medical finding at a physical examination as compared with the baseline assessment will be reported as an AE.

Disease Progression

Disease progression can be considered as a worsening of a patient's condition attributable to the disease for which the Investigational Product (IP) is being studied. It may be an increase in the severity of the disease under study (DUS) and/or increases in the symptoms of the disease. Any event or extended hospitalisation that is unequivocally due to disease progression must not be reported as an SAE unless it is believed that the study drug actively contributed to the progression of the disease (ie, not by way of insufficient therapeutic effect). Insufficient therapeutic effect will be captured as an efficacy outcome. Instances of, or discontinuation due to insufficient therapeutic effect (ie, lack of efficacy) should not be collected as AEs.

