- l Determine patient's disease severity using PORT Score determination and confirm patient meets PORT Risk Class Determination III or IV (see [Appendix D](#))
- m Record resting vital signs, daily, including heart rate, blood pressure (after in a supine position for 5 min), respiratory rate and temperature (oral, rectal, or tympanic), while the patient remains on study treatment, at EOT and TOC. Measure the temperature in the a.m. and p.m. and record the patient's highest daily temperature.
- n Record oxygen saturation at baseline, daily while patient remains on the study drug therapy, at the EOT visit, and if medically indicated at the TOC visit
- o Obtain 12-lead ECGs:
- Baseline: three 12-lead ECGs separated by at least 1 minute, within a 15 minute period
 - Day 3 (± 1 day), EOT and TOC: one 12-lead ECG recording within 60 minutes of the end of Infusion 2
- p Chest X-ray / CT scan (see App. E) NOTE: these are not obtained at TOC or LFU for previous treatment failures
- q Laboratory tests include: haematology, clinical chemistry, PT/INR, PTT, RDW, MCV, reticulocyte count, haptoglobin, urinalysis and urine microscopy at times indicated in [Table 1](#), (see [Appendix G](#) and Laboratory Manual).
- r EOT Laboratory tests not performed if previous tests were within prior 24 hours
- s Additional Laboratory tests (blood): Reference: [Appendix G](#) and Laboratory Manual
- Baseline: c-reactive protein
 - Baseline and LFU: serology for atypicals
 - Baseline, EOT and TOC: direct Coombs
 - Arterial blood gas (ABG) to measure pH, P_aO_2 & P_aCO_2 , (according to investigator's judgment eg, hypoxic)
- t CLcr will be calculated at times indicated in [Table 1](#) and as medically indicated
- u Urine pregnancy test for women of child-bearing potential and those who are <2 years postmenopausal
- v EOT laboratory tests not performed if previous laboratory tests were within prior 24 hours
- v Results of *L. pneumophila* urinary antigen test (UAT) must be available before randomisation. Patients with a positive result are excluded from participation
- w Obtain sputum specimen, culture, perform Gram's stain and susceptibility testing (see Laboratory Manual):
- At baseline
 - Repeat if medically indicated.

- At EOT (if deemed a treatment failure),
 - At TOC (if deemed a treatment failure and was not previously categorized a failure),
 - At LFU if medically indicated (eg, patient experiencing a relapse)

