- ^x Obtain pleural fluid specimen only if medically indicated on any study day, repeat samples are not required
- ^y Obtain blood sample to culture and perform susceptibility testing (see Laboratory Manual):
- At baseline,
 - If medically indicated (e.g., persistent or new signs and/or symptoms)
 - Repeat until negative and at EOT and TOC if the previous blood culture was positive
 - At EOT (if negative at previous visit but medically indicated and/or deemed a treatment failure at EOT)
 - At TOC (if not a failure at EOT but medically indicated and/or deemed a treatment failure at TOC)
 - At LFU if medically indicated (e.g., patient is experiencing a relapse)
- ^z Additional information is required for AEs of haemolytic anaemia, acute renal failure and seizure/confusion and DILI(drug-induced liver injury), irrespective of seriousness
- ^{aa} Study drug infusion may occur on the same calendar day as the EOT, but must be completed before EOT assessments begin
- ^{bb} For those patients that have consented to participate in the optional PK portion of the study, obtain their written consent. Collect plasma samples from the dose which is the most convenient for collecting plasma samples on Day 3 of treatment (see Table 2). Start and stop times of Infusions 1 and 2 for the PK sampling daily dose on Day 3 must be recorded. The plasma sample handling and processing instructions will be provided in a separate, detailed Laboratory Manual

Table 2 PK sample schedule

Study Day / Dose	PK Sampling Time
Day 3 / Dose convenient for plasma samples collection ^c	Plasma samples for drug analysis will be obtained at the following times on Day 3 following the administration of the dose convenient for plasma samples collection from patients participating in the optional PK substudy ^a : 
 • Within 15 minutes prior to the start of Infusion 1^b (trough) • Within 5 minutes following the end of Infusion 2 (peak) • Between 1 and 3 hours after the end of Infusion 2 • Between 4 and 8 hours after the end of Infusion 2

^a It is expected that 200 patients will participate in the optional PK sub-study which should produce PK samples from approximately 100 patients randomised to each treatment group. Additional information on sample collection, processing and shipment can be found in a separate Laboratory Manual.

^b See Section 5.5.2 and Table 4 for infusion information

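### Extra data on haemolytic anaemia, acute renal failure and liver injury start from a reported AE, but the laboratory rule can stop asymptomatic, non-serious cases from being reported as one

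*Protocol*

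**What the plan says.** Two places in the protocol set up the special collection. Section 6.4.3 (Recording of adverse events) asks for additional information "when an AE of seizure, haemolytic anaemia, acute renal failure and DILI (drug-induced liver injury) is reported, irrespective of seriousness". Table 1 footnote z, in Section 3.1, says "Additional information is required for AEs of haemolytic anaemia, acute renal failure and seizure/confusion and DILI(drug-induced liver injury), irrespective of seriousness". The footnote includes confusion and Section 6.4.3 does not.

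Later in Section 6.4.3, under AEs based on examinations and tests, deterioration from baseline in scheduled laboratory values, vital signs and ECGs "should therefore only be reported as AEs if they fulfil any of the SAE criteria or are the reason for discontinuation of treatment". The stated reason is that these results are summarised in the study report in any case. The same part adds that, where there are no clinical signs or symptoms, "clinically relevant deteriorations in non-mandated parameters should be reported as AE(s".

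The general AE definition in Section 6.4.1 is wider. It counts as a possible AE "the abnormal results of an investigation (eg, laboratory findings, electrocardiogram" among other abnormal results.

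**The concern.** The special collection is meant to apply whatever the seriousness, but it begins only once an AE has been reported. For events that show first in scheduled blood tests, the laboratory rule makes seriousness or discontinuation a condition of that report. The two rules pull in opposite directions, and nothing in the protocol says which one governs the events of interest.

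At stake is case-level safety information: the clinical context of a silent haemolysis, a creatinine rise or a moderate enzyme rise. Laboratory tables show that a value was abnormal, but they do not supply that context, and no analysis can restore what was never collected. The protocol itself treats these risks as relevant. Section 1.4.2 lists a positive Coombs' test and raised hepatic enzymes as typical class effects, and nephrotoxicity and haemolytic anaemia among infrequent severe reactions.

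**Working it through.** No arithmetic on rates, power or sample size applies. The check sets the rules side by side and follows a case through them.

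**1. Are the revealing tests scheduled ones?** Yes.
- Table 1 footnote q: "Laboratory tests include: haematology, clinical chemistry, PT/INR, PTT, RDW, MCV, reticulocyte count, haptoglobin, urinalysis and urine microscopy".
- Table 1 footnote s: "Baseline, EOT and TOC: direct Coombs".
- Table 1 footnote t: "CLcr will be calculated at times indicated in" Table 1, that is, at baseline, Day 3 and EOT.
- Appendix G puts creatinine, ALT, AST and bilirubin in the chemistry panel.

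The restriction in Section 6.4.3 therefore covers the tests by which all three conditions would be seen.

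**2. Does the restriction make an exception?** No. The sentence on asymptomatic deterioration is limited to non-mandated parameters, which supports the literal reading that asymptomatic deterioration in a mandated test is not an AE unless one of the two criteria is met.

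**3. What happens to a non-serious case that does not stop treatment?**
- *With symptoms:* the sign or symptom is an AE. The special collection starts if the investigator records the diagnosis.
- *No symptoms, AST or ALT ≥3×ULN with total bilirubin ≥2×ULN:* additional information is collected under the Hy's Law sentence in Section 6.4.3, which does not depend on a reported AE.
- *No symptoms, haemolysis, renal decline, or liver injury below those thresholds:* read literally, not an AE, so the special collection is not triggered.

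**4. When can the discontinuation criterion apply?** The main laboratory panel is scheduled at baseline, Day 3, EOT and TOC, giving three post-baseline visits. Table 1 footnote aa requires dosing to be complete before EOT assessments start, and TOC is 8 to 15 days after the last dose. In a patient who completes the course, an abnormality first seen at EOT or TOC cannot be the reason for stopping.
- Main panel: 2 of 3 post-baseline visits (EOT, TOC) cannot meet the criterion.
- Direct Coombs: 2 of 2 (EOT, TOC).
- Creatinine clearance as scheduled: 1 of 2 (EOT; Day 3 can).

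For early stoppers it is different. Table 1 footnote b places the EOT assessments on the day of discontinuation, and Section 5.8 names a clinically significant laboratory abnormality as a reason to stop. For them the criterion can be met at EOT.

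**5. How many patients?** The protocol gives no rate of asymptomatic abnormality in these tests, so no number can be derived.

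**The case against.** The strongest reply is that the two rules do not strictly contradict each other. The special collection is conditional on a reported AE and does not promise to find every laboratory case. The restriction concerns deterioration in a value, whereas haemolytic anaemia, acute renal failure and DILI are diagnoses. Section 6.4.3 prefers diagnoses and clinical terms, so an investigator who diagnoses haemolytic anaemia could report it. This is a fair reading, but the text does not say that a diagnosis resting only on scheduled tests escapes the restriction, and 50 to 56 centres could apply it differently.

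The second reply is that other routes exist, and they do:
- Sections 5.5.3.1 and 5.5.3.2 require contact with the study physician if creatinine clearance is 30 mL/min or less during treatment, in either arm.
- Section 11.2.1 provides for an expert review of laboratory data for OAEs.
- Section 12.2.4.3 provides shift tables and counts of clinically significant results.
- Section 6.4.2 and Appendix B allow important medical events, including some blood dyscrasias, to count as serious.

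These routes narrow the gap. None is stated to start the additional collection for an asymptomatic, non-serious haemolysis, renal decline or milder liver injury.

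Thirdly, the restriction is a deliberate convention to avoid duplicating results, and the eCRF instructions mentioned in Section 10 are not shown. Both points stand. They are reasons to add a narrow exception and keep the general rule.

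A reader might infer that no non-serious laboratory-detected case is captured, or that only serious cases would reach the special-interest data. The documents do not support this: symptomatic cases, recorded diagnoses, treatment-stopping cases and Hy's Law values all remain, and many of these can be non-serious. Nor do they support the idea that the discontinuation criterion can never apply at EOT, as step 4 shows.

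**Conclusion.** The concern holds in a narrow form. Cases that are asymptomatic, non-serious, do not stop treatment, are seen only in scheduled tests and are not recorded as a diagnosis may go unreported as AEs and so miss the additional information that the protocol wants whatever the seriousness. For liver injury this applies below the Hy's Law thresholds. For renal decline, the clearance contact rule offers a separate route to the sponsor during treatment. The laboratory values themselves are not lost.

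The conclusion assumes that sites apply the laboratory restriction as written and that no other instruction overrides it. The count of affected patients is unknown. Efficacy conclusions are untouched, and Section 12.2.4 plans no inference on safety. The difference between the two trigger lists over confusion is a separate small inconsistency, plain on the page. The point is a cheap improvement.

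**What to change.** Reconcile Table 1 footnote z with the two parts of Section 6.4.3 by adding one sentence to the part on AEs based on examinations and tests, for example: *As an exception, laboratory deterioration that the investigator considers to represent haemolytic anaemia, acute renal failure or drug-induced liver injury is recorded as an AE, whether or not it is serious or led to discontinuation.*

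Use one list of trigger events in Table 1 footnote z and Section 6.4.3, with the sponsor deciding whether confusion belongs in it, and carry the same wording into the eCRF instructions.

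The cost is about two sentences, a few more AE forms, and slightly higher reported AE rates in both arms. Dosing, visits and tests stay the same.
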